6.3 Pharmacokinetics/pharmacodynamics

6.3.1 Pharmacokinetics

Analyses will be performed based on the FAS.

The following will be determined at several timepoints according to Integrated Protocol Table 9-1:

- LNG concentrations in plasma
- Sex hormone binding globulin (SHBG) concentrations in serum

Data will be analyzed descriptively (including number of measurements, geometric mean with geometric standard deviation and coefficient of variation, arithmetic mean with arithmetic standard deviation and coefficient of variation, minimum, maximum and median) by time point (i.e. Visit 2 to Visit 8). Means at any time point will be calculated only if at least two-thirds of the individual data were measured and were above the LLOQ. For the calculation of the mean value a data point below LLOQ will be imputed by one-half of this limit. In tables showing mean values, where values below LLOQ are included in the calculation of mean values, these means will be marked.

The individual PK concentrations will be presented in the subject data listing.

Geometric mean concentration (\pm geometric standard deviation) curves of LNG and SHBG will be plotted versus time point using a linear and semi-logarithmic scale.

PK concentrations determined after Mirena expulsion/removal will not be included in the descriptive analyses and plots, but only be listed.

Furthermore, the residual content of LNG in used Mirena devices will be determined from all subjects at the end of treatment (i.e. from those who complete the 3 years in the study and from those who discontinue the study treatment prematurely). Data will be listed per subject and time point and individual data will be plotted versus time post baseline using a linear scale.

Residual contents with a partially missing or completely missing date of Mirena expulsion/removal will not be included in the plot, but only be listed.

Population PK analysis will be performed after Year 6, after Year 7 and at the end of study by the Modeling & Simulation (M&S) expert. A separate M&S Analysis Plan will be provided prior to the beginning of the population PK analysis by the M&S expert, including details of the planned model development and analysis. The results will be reported in a separate M&S Report by the M&S expert. A summary of the results will be provided in the Clinical Study Report.

6.3.2 Pharmacodynamics

Not applicable.

6.4 Safety

All safety variables will be analyzed based on the SAF, unless otherwise stated.

The main safety variable is the incidence of treatment-emergent AEs (both serious and non-serious). Treatment-emergent AEs are defined as any AEs occurring during the 'extension treatment period' starting at Day 1 of Year 6 of Mirena use. Further data rules are described in Section 4.7.

All AEs will be classified using MedDRA. The latest available version at the time of coding will be used. The results will be summarized on the level of SOC and PT, unless stated otherwise.

6.4.1 Pretreatment adverse events

Pretreatment AEs will be summarized by SOC and PT.

Pretreatment serious AEs (SAEs) will only be listed.

6.4.2 Treatment-emergent adverse events

The following treatment-emergent AEs will be summarized by SOC and PT:

- AEs, by year of occurrence (6th / 7th / 8th year) and overall
- Study-drug related AEs (with causality as assessed by investigator)
- AEs causing discontinuation of study drug
- Study-drug related AEs (with causality as assessed by investigator) causing discontinuation of study drug
- AEs by outcome
- AEs by intensity

The overall summary tables will be displayed by year of occurrence (6th / 7th / 8th year) and overall, whereas AEs will be allocated to the year of occurrence as described in Section 4.7. For the calculation of the percentages by year of occurrence, only the number of subjects that were still under treatment at the beginning of the respective time interval (treatment year) will be used as the denominator.

The following treatment-emergent SAEs will be summarized by SOC and PT:

- SAEs
- Study-drug related SAEs (with causality as assessed by investigator)

6.4.2.1 Perforation rates

As described in Integrated Protocol Section 9.6.3.9, perforation by the Mirena must be reported as an SAE. If a perforation is diagnosed, Mirena must be removed and the subject must discontinue study treatment and the study.

Perforations will be identified from the AEs recorded on the eCRF coded by MedDRA as one of the following:

- Preferred Term “Uterine perforation”
- Preferred Term “Embedded Device”,
- Preferred Term “Fallopian tube perforation”,
- Lowest Level Term “Extrauterine intra-abdominal localisation of IUD”,
- Lowest Level Term “Extrauterine intra-abdominal localization of IUD”,

- Lowest Level Term “IUD migration”,
- Lowest Level Term “Device migration”,
- Lowest Level Term “Device dislocation into abdominal cavity”.

The number of subjects with perforation by the Mirena during the ‘extension treatment period’ (starting at Day 1 Year 6) will be summarized in a frequency table, overall and by parity.

In addition, the time from Day 1 Year 6 to perforation will be analyzed using the Kaplan-Meier estimator. If no perforation occurred in a subject, this is considered a censored observation and the stop date of study drug administration (as defined in Section 4.7) will be used as censoring date.

The estimated proportion of subjects with perforation of the Mirena will be reported for the time points 6 months (5.5 years of Mirena use), 12 months (6 years of Mirena use), 18 months (6.5 years of Mirena use), 24 months (7 years of Mirena use), 30 months (7.5 years of Mirena use), and 36 months (8 years of Mirena use). The cumulative proportion will be estimated as well.

All subjects with perforation by the Mirena will be listed. The listing will contain the parity status as well as the duration from last birth or induced/spontaneous abortion to insertion and the time in days after Day 1 Year 6 when the perforation was discovered.

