6.4 Withdrawal of subjects from study

6.4.1 Withdrawal

Withdrawal criteria

This section was changed in Amendment 1, see Section 15.1.1.4 and 15.1.1.13.

Subjects *must* be withdrawn from the study if any of the following occurs:

- At their own request. At any time during the study and without giving reasons, a subject may decline to participate further. The subject will not suffer any disadvantage as a result.
- Complete or partial expulsion of the Mirena
- Removal of Mirena outside the study procedures
- Pregnancy
- Partial or total perforation of the uterus or cervix by Mirena
- Acute pelvic inflammatory disease (PID) not responding to treatment
- Genital malignancy (e.g., uterine or cervical malignancy)
- Severe arterial disease such as stroke or myocardial infarction (MI)
- Liver tumor (benign or malignant)
- Allergic reaction to the study medication or any of its components
- If, in the investigator's opinion, continuation of the study would be harmful to the subject's well-being
- Should the subject, during the course of the study, develop conditions which would have prevented her entry into the study according to the exclusion criteria, she must be withdrawn immediately if safety is concerned. In other cases, the investigator will decide if there is a conflict with study objectives.
- Participation in any other clinical study during the duration of this study

Subjects *may* be withdrawn from the study if any of the following occurs:

- Coagulopathy or use of anticoagulant
- Migraine, focal migraine with asymmetrical visual loss or other symptoms indicating transient cerebral ischemia
- Exceptionally severe headache
- Marked increase of blood pressure
- Jaundice
- Non-attendance of visits despite the efforts to reach the subject (i.e. if a subject does not attend consecutive visits without a major reason).

- Every effort must be made to have the subject attend these visits in-person. However, once all attempts have been exhausted to have the subject come to the study site, if the subject is unable to do so during the allotted timeframe, the visit may be documented via phone. In these instances, the site should determine the most appropriate means for excluding that a pregnancy has occurred (e.g. home pregnancy test kit, menstrual history, etc). All methods and results regarding determination of pregnancy must be documented.

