9.6.3.8 Presence of Mirena removal threads

This section was changed in Amendment 1, see Section 15.1.1.22.

The presence of the removal threads will be checked at each study visit and recorded in the eCRF.

The investigator will perform pelvic examinations at each study visit to verify the presence of the Mirena removal threads in the appropriate location in the cervical os. If the presence of the removal threads cannot be verified, transvaginal ultrasound (TVUS) is to be performed to verify that the Mirena is in the appropriate intrauterine location and to exclude expulsion or perforation. The subject should be instructed to periodically check the threads by feeling for the threads at the top of the vaginal canal and if, at any time of the study, a subject suspects that the Mirena may have been expelled, she should contact the investigator and the investigator should assess the need for an unscheduled visit to evaluate the location of the Mirena. The subject should be instructed to use non-hormonal back-up method of contraception until it is confirmed that the Mirena is in the proper location.

Subject is **in compliance** with Mirena when:

- Threads are visible, or,
- Threads are not visible (or not checked) but TVUS performed to localize the Mirena shows Mirena to be “In situ” or “Displaced intrauterine”.

Subject is **non-compliant** with Mirena when:

- Threads are not visible, and,
- TVUS performed to localize Mirena shows that the IUS is “Partially or totally expelled into vagina or cervical canal”, “Cervical perforation”, “Myometrial perforation”, “Localization in the peritoneal cavity”, or “Absent”.
- Threads are visible, but TVUS is performed for other reason(s) and Mirena localization is recorded as “Partially or totally expelled into vagina or cervical canal”, “Cervical perforation”, “Myometrial perforation”, “Localization in the peritoneal cavity”.

Non-compliance with Mirena necessitates discontinuation of the subject from the study. In case the IUS is partially expelled, it needs to be removed. In case perforation has occurred, the IUS needs to be removed using appropriate procedures.

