9.6.3.9 Expulsion of Mirena

Total or partial expulsion of the Mirena **will be reported as an AE or SAE, as appropriate** (i.e. meets the criteria for an SAE as specified in Section 9.6.1.1).

Total expulsion is confirmed if Mirena is observed in the vagina, it is not shown in the uterine cavity by ultrasound, and/or the subject confirms that the system was expelled. If, upon pelvic examination, the removal thread(s) cannot be seen, expulsion should be considered and an ultrasound must be performed. Possibilities of cervical or uterine perforations may be

excluded by ultrasound, x-ray or hysteroscopy before making a final diagnosis of total expulsion.

Partial expulsion is diagnosed if the Mirena can be partially seen in the vagina or is displaced in the cervical canal. If Mirena is partially expelled, it must be removed.

Upon total or partial expulsion of Mirena, the subject must discontinue study treatment and the study.

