9.6.3.10 Perforation by Mirena

All perforations (cervical or myometrial perforations or perforations resulting in Mirena localization in the peritoneal cavity) **will be reported as SAEs**.

If a perforation is diagnosed, Mirena must be removed (this may require further intervention such as hysteroscopy or laparoscopy) and the subject must discontinue study treatment and the study.

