6.1.3.5 Compliance

The definition of compliance with Mirena is given in Integrated Protocol Section 9.6.3.8.

The number of subjects compliant and non-compliant, respectively, during the ‘extension treatment period’ (starting at Day 1 Year 6) will be summarized over time in frequency tables, overall and by parity status (no birth vs. at least one birth).

The time from Day 1 Year 6 to (first) non-compliance will be analyzed using the Kaplan-Meier estimator. If no non-compliance occurred in a subject, this will be considered a censored observation and the stop date of study drug administration (as defined in Section 4.7) will be used as censoring date.

The estimated proportion of subjects who are compliant will be reported for the time points 6 months (5.5 years of Mirena use), 12 months (6 years of Mirena use), 18 months (6.5 years of Mirena use), 24 months (7 years of Mirena use), 30 months (7.5 years of Mirena use), and 36 months (8 years of Mirena use). The cumulative proportion will be estimated as well.

The number of subjects in each sub-category will be summarized over time in frequency tables, overall and by parity, as follows:

- Compliant with Mirena
 - Threads visible
 - Threads not visible and transvaginal ultrasound (TVUS) performed => location of Mirena:
 - In situ
 - Displaced, intrauterine
- Non-compliant with Mirena
 - Threads not visible and TVUS performed => location of Mirena:
 - Partially or totally expelled into vagina or cervical canal
 - Cervical perforation
 - Myometrial perforation
 - Migration to the peritoneal cavity

- Absent
- Other
- Threads visible and TVUS performed => location of Mirena:
 - Partially or totally expelled into vagina or cervical canal
 - Cervical perforation
 - Myometrial perforation
 - Migration to the peritoneal cavity
 - Other

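### The perforation rate rests on coded adverse-event terms alone, some of which do not establish perforation, and it is not reconciled with the device location that the SAP already tabulates

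*SAP*

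**What the plan says.** **Protocol definition.** Section 9.6.3.10 gives the scope as "All perforations (cervical or myometrial perforations or perforations resulting in Mirena localization in the peritoneal cavity", and all of these are to be reported as SAEs. The mandatory withdrawal criterion in 6.4.1 is worded to match, with cervix and incomplete perforation both included: "Partial or total perforation of the uterus or cervix by Mirena". The perforation rate is a named safety variable in protocol 10.3.1.2.

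**What the protocol treats as something else.** Under 9.6.3.8 a device displaced inside the uterus leaves the woman compliant; the relevant criterion begins "Threads are not visible (or not checked) but TVUS performed to localize the Mirena shows Mirena to be" and goes on to name in situ and displaced intrauterine positions. Under 9.6.3.9, "Partial expulsion is diagnosed if the Mirena can be partially seen in the vagina or is displaced in the cervical canal".

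**SAP rule.** Section 6.4.2.1 states: "Perforations will be identified from the AEs recorded on the eCRF coded by MedDRA as one of the following". The list has three preferred terms (*Uterine perforation*, *Embedded Device*, *Fallopian tube perforation*) and five lowest level terms: extrauterine intra-abdominal localisation in two spellings, *IUD migration*, *Device migration*, and device dislocation into the abdominal cavity. Events so identified feed a frequency table, a Kaplan-Meier analysis and a listing. For the SAE reporting rule the section cites protocol 9.6.3.9, which is the expulsion section; perforation is 9.6.3.10.

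**Location data elsewhere in the SAP.** Section 6.1.3.5 tabulates device location at transvaginal ultrasound. Its non-compliant categories include "Cervical perforation", myometrial perforation and migration to the peritoneal cavity. Section 4.7 uses the same compliance information to set the date the device was last known in situ.

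**The concern.** The rate is defined by how an event was coded, and nothing in 6.4.2.1 asks whether the event meets the protocol's definition. That leaves two openings. A migration term can bring in a device that the protocol would call compliant or partially expelled. A cervical perforation is counted only if it codes to a listed term, and the SAP does not say whether it does.

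Meanwhile a variable that uses the protocol's own categories is analysed in another section for the same period, starting at Day 1 of Year 6, with no rule for comparing the two. One study report could therefore contain two perforation counts, or show one woman as compliant in one table and perforated in another. Protocol section 3 describes perforation as an important but rare risk, so a single classification decision is a visible part of the result.

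**Working it through.** The documents state no expected perforation rate, precision or power, so there is no planned figure to reproduce. The check is a comparison of definitions, followed by an illustration of what one case is worth.

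**Step 1. How the same event is treated in each place.**

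| Situation | Protocol | SAP 6.1.3.5 | SAP 6.4.2.1 |
|---|---|---|---|
| Cervical perforation, seen at ultrasound and reported | Perforation, SAE | Non-compliant, cervical perforation | Counted only if it codes to a listed term; not determinable from the documents |
| Location recorded as a perforation, event coded outside the list | Perforation | Non-compliant, perforation category | Not counted |
| Device displaced inside the uterus, event coded to a migration term | Compliant | Compliant, displaced intrauterine | Counted |
| Device displaced into the cervical canal, event coded to a migration term | Partial expulsion | Non-compliant, expelled | Counted |
| Device partly in the myometrium, event coded to *Embedded Device* | Perforation, if judged partial perforation | Depends on recorded location | Counted |

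Rows two to four are discordant by construction if such cases arise. Row one is open. Row five may be correct.

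**Step 2. Restriction within the list.** Three of the five lowest level terms state an abdominal location (the two spellings of extrauterine intra-abdominal localisation, and dislocation into the abdominal cavity). The two migration terms do not. They are therefore the clearest entries that do not by themselves meet protocol 9.6.3.10.

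**Step 3. Seriousness.** The protocol makes every perforation an SAE. The SAP selects from AEs with no seriousness condition, so a non-serious event coded to a migration or embedded-device term enters the rate without further check.

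**Step 4. What one case is worth (illustration only).** Input: 360 women planned for the treatment period (protocol section 5). Crude proportion = x/n, with exact Clopper-Pearson 95% limits.

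- x = 0: 0.00%, upper limit 1 − 0.025^(1/360) = 1.02%.
- x = 1: 1/360 = 0.28%, limits 0.01% to 1.54%.
- x = 2: 2/360 = 0.56%, limits 0.07% to 1.99%.

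Each case wrongly counted or left out moves the crude proportion by 0.28 percentage points. Going from none to one moves the upper limit from 1.02% to 1.54%. SAP 6.4.2.1 does not call for confidence limits on this rate; they are shown only to give scale.

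**The case against.** The best defence is that adverse events are a reasonable primary source. The protocol requires every perforation, cervical ones included, to be reported as an SAE. Ultrasound is not part of the routine gynecological examination (9.6.3.3); it is done when the threads cannot be verified or for other reasons (9.6.3.8). Location is thus recorded for only some women and cannot replace event reports. That stands, and the fix keeps both sources.

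A reader might infer that cervical perforations will be missed. The documents do not support this. They do not contain the MedDRA hierarchy, and a cervical case might code to *Uterine perforation*. What is shown is that no listed term names the cervix and that the SAP does not say where such a case goes.

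A reader might also infer that *Embedded Device* is a mistake. It may be there to catch partial perforation, which the withdrawal criterion in 6.4.1 includes, so removing it could under-count. It needs confirmation rather than deletion.

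The defence can add that the list was updated in SAP v2.0 (SAP section 7), that for dislocation it names only the abdominal cavity, and that partial expulsion has its own category on the removal page (SAP 6.1.3.3). These points suggest care was taken, but no reason for the update is given and they place no limit on the migration terms. Protocol 9.6.1.1 also provides for medical review of the events in section 9.6.3. That text concerns seriousness and refers to a separate plan, so it does not establish case confirmation for this rate.

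Finally, discordant cases would be partly visible: perforation cases are listed individually, ultrasound data are listed (SAP 6.4.6.3) and SAEs are tabulated. That limits the harm, but it leaves the reader to do the reconciliation.

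**Conclusion.** The point holds in a limited form. The rule in SAP 6.4.2.1 is not tied to the protocol's definition of perforation. It admits two migration terms without confirmation, leaves the handling of cervical cases unstated, and can disagree with the perforation categories in 6.1.3.5. The error could go in either direction, and its size cannot be derived, because the documents do not say how many displaced, migrated or embedded devices to expect. The figure of 0.28% per case assumes 360 women in the denominator and a crude proportion; the Kaplan-Meier estimate would differ somewhat with censoring.

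This is a descriptive safety rate with no hypothesis or threshold attached. A reader might infer from the shared location data that the primary analysis is at risk, but the perforation count does not enter the Pearl Index, so nothing here changes it.

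**What to change.** In SAP 6.4.2.1:

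1. Define a perforation case by protocol 9.6.3.10. Take cases from either source: an AE or SAE reported as perforation at any site including the cervix, or a recorded location of cervical perforation, myometrial perforation or migration to the peritoneal cavity.
2. Keep the MedDRA list as a trigger for finding cases, and state where cervical perforation codes.
3. Check events under *IUD migration*, *Device migration* and *Embedded Device* against the recorded location or the removal finding before counting them. Where neither is available, list them and show the rate with and without them.
4. Reconcile the result with the perforation categories in 6.1.3.5 and list discordant cases.
5. Correct the protocol cross-reference from 9.6.3.9 to 9.6.3.10.

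The cost is SAP wording, a cross-check against location data that the SAP already analyses, and a short medical review of what should be a few discordant cases. The documents do not show whether a perforation seen at removal is captured as a data field, which is why step 3 provides for cases that cannot be checked.

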6.4.2.2 Pelvic inflammatory disease

As described in Integrated Protocol Section 9.6.3.11, any case of pelvic inflammatory disease (PID) will be reported as an AE or SAE on the AE eCRF as well as on the pelvic inflammatory disease eCRF.

PID will be presented as part of the AE summary tables described in Section 6.4.2.

Details recorded on the pelvic inflammatory disease eCRF will be listed only. A diagnosis of PID is made if response to the following questions in the eCRF is a “yes”: “Were the criteria for PID diagnosis met?” and/or “Laparoscopy confirmed PID?”.

6.4.3 Uterine bleeding / bleeding pattern

Recording and evaluation of bleeding data:

The occurrence of uterine bleeding will be recorded every day during the study treatment phase using eDiaries provided by the sponsor. The recording will start at the baseline visit and will be continued daily until Mirena is removed. Subjects are asked to rate their uterine bleeding in the past 24 hours on a daily basis according to the bleeding intensity definitions presented in Integrated Protocol Section 9.6.3.12 and Integrated Protocol Table 9–3.

Uterine bleeding data during the ‘extension treatment period’ starting at Day 1 of Year 6 of Mirena use will be analyzed according to the sponsor’s BPD “Recording and evaluation of bleeding data” (RD-SOP-1107) (1). Bleeding diary data prior to the ‘extension treatment

period' will not be included in the analyses described in this section. That means, for subjects who had her baseline visit prior to Day 1 Year 6, bleeding diary data between the baseline visit and Day 1 Year 6 will be excluded; for subjects who had their baseline visit after Day 1 Year 6, bleeding diary data between Day 1 Year 6 and baseline visit will not be recorded and will be considered as missing data entries. Bleeding diary data after Mirena expulsion/removal will not be included in the statistical analysis. Bleeding diary data after the date of premature discontinuation of study treatment period will not be included in the statistical analysis.

Besides the registration of absolute number of bleeding days, bleeding/spotting episodes will also be assessed according to the sponsor's bleeding intensity codes and the WHO definitions as provided in Integrated Protocol Section 10.3.2.3.2 and Integrated Protocol Table 10–2. This is possible because of the direct eDiary entry.

In addition to the WHO definitions, a “bleeding episode” is defined as day(s) with bleeding / spotting of which at least one day is of intensity 3 or higher, preceded and followed by at least 2 bleed-free days. There are examples given in the sponsor's BPD Section 1.4.1 which illustrate the advantage of this procedure. Another example is given in Integrated Protocol Section 10.3.2.3.2.

The bleeding patterns will be described using the reference period method recommended by the WHO, as given in the sponsor's BPD Section 1.4.3.

Based on daily uterine bleeding data obtained from the eDiary, the bleeding pattern will be reported using reference periods of 28 and 90 days. The first 28-day and 90-day reference period, respectively, will start at Day 1 of Year 6 of Mirena use. For each subject and for each period, the number of bleeding/spotting days and bleeding/spotting episodes will be calculated. If the bleeding intensity is recorded as light, normal or heavy, this will be considered as “bleeding”.

Handling of missing bleeding intensities and censored eDiaries:

Details on how to handle missing bleeding intensities and censored eDiaries are given in Section 4.4.

Summary of bleeding pattern indices:

For each subject and for each 28-day reference period and each 90-day reference period, the following bleeding pattern indices will be calculated (compare to sponsor's BPD Section 1.4.3):

- number of subjects with at least one bleeding/spotting day
- number of subjects with at least one bleeding (excluding spotting) day
- number of bleeding / spotting days
- number of bleeding days (excluding spotting-only days)
- number of spotting-only days
- number (mean length, maximal length) of bleeding / spotting episodes (will only be calculated for those subjects who have at least 1 bleeding/spotting episode)

- number (mean length, maximal length) of spotting-only episodes (will only be calculated for those subjects who have at least 1 spotting-only episode)

Furthermore, for each 90-day reference period the following bleeding indices will be provided according to the WHO criteria:

- number of subjects with amenorrhea, defined as no bleeding/spotting throughout the reference period
- number of subjects with prolonged bleeding, defined as subjects with bleeding/spotting episodes lasting more than 14 days
- number of subjects with frequent bleeding, defined as subjects with more than 5 bleeding/spotting episodes
- number of subjects with infrequent bleeding, defined as subjects with 1 or 2 bleeding/spotting episodes
- number of subjects with irregular bleeding, defined as subjects with 3 to 5 bleeding/spotting episodes and less than 3 bleeding/spotting-free intervals of 14 days or more
- number of subjects with normal bleeding / none of the above

